7.6.4.2 Death

Number of subjects who died and the cause of death will be presented for each treatment group for the ITT population. The proportion of subjects who died along with 95% exact binomial CI (Clopper-Pearson) will be presented for each treatment group. Two-sided 95% CI will also be presented for the difference in percent of subjects who died between treatment groups with an approximate normal distribution. The Fisher's exact test will be used to compare the proportion of subjects who died. The two-sided p-value for the Fisher's exact test will be presented.

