3 INTRODUCTION

3.1 Coronavirus-19 (COVID-19)

Beginning in December 2019, Chinese scientists isolated a novel coronavirus, severe acute respiratory syndrome coronavirus 2 (SARS-CoV-2) from patients with virus-infected pneumonia which was later designated as coronavirus disease 2019 (COVID-19) by the World Health Organisation (WHO) (Zhou et al., 2020 [2]; Phelan et al., 2020 [3]).

Approximately 14% of those affected with this virus will develop severe disease requiring hospitalization and oxygen support; 5% will require admission to the intensive care unit (Handel et al., 2020 [4]). Severe cases may be complicated by acute respiratory disease syndrome (ARDS), sepsis and septic shock, and multi-organ failure, including acute kidney injury and cardiac injury. Risk factors for death include older age and co-morbid disease such as hypertension and diabetes (Zhou, et al., 2020 [2]). This means that most patients will be treated as out-patients. Reducing viral load in this environment is critically important for both the subjects themselves by preventing worsening of symptoms and possibly avoiding hospitalization, but also to reduce the transmission of the disease to others in the patients' households and their communities.

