7.2 Inclusion criteria

1. Willing and able to provide informed consent for the trial, written, electronic, verbal or other method deemed acceptable by the institution and IRB.
2. 18 years of age or older.
3. Laboratory-confirmed SARS-CoV-2 infection as determined by real time polymerase chain reaction (RT-PCR) or other FDA-approved commercial or public health assay.
4. Out-patient (never hospitalized as an in-patient for COVID-19 or was evaluated/treated for COVID-19 only in the Emergency Room with a stay of < 24 hours).
5. The effects of brequinar on the developing human fetus are unknown. For this reason, women of child-bearing potential and men must agree to use adequate contraception (hormonal or barrier method of birth control; abstinence) prior to study entry and for the duration of study participation. Should a woman become pregnant or suspect she is pregnant while she or her partner is participating in this study, she should inform her treating physician immediately. Men and women treated or enrolled on this protocol must also agree to use adequate contraception for the duration of study participation, and for 90 days after completion of brequinar administration.
6. Male subjects must agree to refrain from sperm donation and female subjects must agree to refrain from ovum donation from initial study drug administration until 90 days after the last dose of brequinar.
7. At least one COVID-19 symptom including but not limited to fever, cough, sore throat, malaise, headache, muscle pain, gastrointestinal symptoms, shortness of breath, dyspnea, anosmia, dysgeusia, or other symptom commonly associated with COVID-19 in the opinion of the investigator. Symptom onset must be ≤ 7 days prior to first dose. Subject must have one or more symptoms at first dose.
8. Able to swallow capsules.

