2.3 Sample Size and Power

Formal sample size calculations are not applicable for this proof-of-concept study. The sample size of approximately 100 subjects planned to be entered in this trial is expected to be adequate to provide safety and efficacy information to advise future study design. Subjects who meet all of the inclusion and none of the exclusion criteria will be enrolled in the study until approximately 100 subjects have completed the study.

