7.1 General Principles

All data processing, summarization and analyses will be performed using Covance's SAS Environment / Version 9.3 (or later) of the SAS® statistical software package.

The following principles will be applied to all tables, figures, and listings (TFLs) unless otherwise stated:

Principle	Value
Significant tests	Two-sided and use a 5% significance.
Treatment group labels and order presented	SOC + Brequinar 100 mg SOC + Placebo
Tables	Data in summary tables presented by treatment group, assessment and visit (where applicable), unless otherwise specified.
Listings	All data collected presented by treatment group, site, subject, assessment and visit (where applicable), unless otherwise specified.
Descriptive summary statistics for continuous variables	Number of subjects/observations (N), mean, standard deviation (SD), median and range.
Descriptive summary statistics for categorical variables	Frequency counts and percentages [n (%)]
Denominator for percentages	Number of subjects in the analysis population, unless stated otherwise in table shell(s)
Include "Missing" as category	Yes, when the number missing is greater than zero for at least one treatment group.
Display for 0 percentages	Blank
Display to one more decimal place than collected value	Mean Standard Error Mean Difference Median
Display to two more decimal places than collected value	Standard Deviation Confidence Interval
Limit of precision for displays	3 decimal places
Date Format	DDMMYYYY
Dictionary names and versions	The dictionary names and versions will be included in a footnote in all AE, medical history, prior and concomitant medication TFLs that present coded terms from the dictionaries.

Time to event or duration of event endpoints will be based on the actual date rather than Visit Day.

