7.6.4 Secondary Clinical Analysis

7.6.4.1 Hospital Admission

Subjects requiring hospital admission as an inpatient for >24 hours will be analyzed in the ITT population. Number and proportion of subjects requiring hospital admission along with 95% exact binomial CI (Clopper-Pearson) will be presented for each treatment group. Two-sided 95% CI will also be presented for the difference in percent of subjects requiring hospital admission between treatment groups with an approximate normal distribution. The Fisher's exact test will be used to compare the proportion of subjects requiring hospital admission. The two-sided p-value for the Fisher's exact test will be presented.

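### With no deaths, the planned normal-approximation interval for the mortality difference collapses to (0%, 0%); with one or two deaths it is too narrow

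*SAP*

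**What the plan says.** SAP 7.6.4.2 plans three inferential summaries for deaths in the ITT set.

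- Within each arm: "The proportion of subjects who died along with 95% exact binomial CI (Clopper-Pearson) will be presented for each treatment group".
- For the difference between arms: "Two-sided 95% CI will also be presented for the difference in percent of subjects who died between treatment groups with an approximate normal distribution".
- As a test: "The Fisher's exact test will be used to compare the proportion of subjects who died".

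SAP 7.6.4.1 repeats the scheme for admissions, with an interval for the "difference in percent of subjects requiring hospital admission between treatment groups with an approximate normal distribution". Neither section states a variance formula, a continuity correction, or what to do with zero or very few events.

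All-cause mortality through Day 29 is a secondary endpoint (SAP 3.2). The documents give no expected number of deaths: under SAP 2.3, "Formal sample size calculations are not applicable for this proof-of-concept study". Protocol v5.0 section 7.1 plans about 50 subjects per arm. Section 7.2 restricts entry to subjects described as "Out-patient (never hospitalized as an in-patient for COVID-19 or was evaluated/treated for COVID-19 only in the Emergency Room".

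**The concern.** Exact methods were chosen for the within-arm intervals and for the test, but not for the one quantity that compares the arms. A normal approximation estimates its standard error from the observed proportions, so it fails when those are at or near zero. In a small out-patient trial that is a likely outcome for deaths.

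If nobody dies, the interval for the difference is (0.0%, 0.0%). Taken at face value it rules out any mortality difference, although the same table would allow up to 7.1% mortality in either arm. This interval is the only planned between-arm effect estimate for a named secondary endpoint, and SAP 2.3 says the trial is meant to inform the design of later studies.

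**Working it through.** **Inputs.** n = 50 per arm (Protocol v5.0, 7.1); ITT is all randomized subjects (SAP 5.3); 95% two-sided intervals, z = 1.96. Death rates are assumptions, shown as a range. For admissions, the documents' only figure is the background statement in Protocol 3.1: "Approximately 14% of those affected with this virus will develop severe disease requiring hospitalization and oxygen support". The plan states no interval, event count or power, so there is no figure of its own to reproduce. Differences are brequinar minus placebo.

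**Formulas.**
- Wald: (p1 - p2) ± 1.96 × √[p1(1 - p1)/50 + p2(1 - p2)/50].
- Newcombe, with Wilson limits (l, u) for each arm: lower = (p1 - p2) - √[(p1 - l1)² + (u2 - p2)²]; upper = (p1 - p2) + √[(u1 - p1)² + (p2 - l2)²].

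**No deaths.**
- Wald: the standard error is √(0 + 0) = 0, giving (0.0%, 0.0%). A pooled standard error is also 0.
- Per-arm Clopper-Pearson upper limit: 1 - 0.025^(1/50) = 7.1%.
- Newcombe: the Wilson upper limit is 1.96²/(50 + 1.96²) = 3.84/53.84 = 7.1%, giving (-7.1%, 7.1%). Miettinen-Nurminen gives (-7.2%, 7.2%).

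**0 v 1.** The difference is -2.0%. SE = √(0.02 × 0.98/50) = 0.0198, and 1.96 × 0.0198 = 3.9 points, so Wald is (-5.9%, 1.9%).

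| Deaths | Wald | Newcombe |
|---|---|---|
| 0 v 0 | (0.0%, 0.0%) | (-7.1%, 7.1%) |
| 0 v 1 | (-5.9%, 1.9%) | (-10.5%, 5.3%) |
| 1 v 1 | (-5.5%, 5.5%) | (-8.7%, 8.7%) |
| 1 v 2 | (-8.7%, 4.7%) | (-11.6%, 7.0%) |

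**Coverage.** These figures sum over the full joint binomial distribution. P(0 v 0) = (1 - p1)^50 × (1 - p2)^50; for 0.5% v 1% this is 0.995^50 × 0.99^50 = 0.471.

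| Assumed true rates | P(0 v 0) | Wald coverage | Newcombe coverage | Mean width, Wald v Newcombe (points) |
|---|---|---|---|---|
| 0.5% v 1% | 47% | 53% | above 99% | 4.8 v 15.4 |
| 1% v 2% | 22% | 77% | above 99% | 8.1 v 16.4 |
| 2% v 4% | 5% | 86% | above 99% | 12.5 v 18.4 |

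**Where the misses come from.** At 0.5% v 1%, essentially all 47.1 points of non-coverage are the 0 v 0 result. At 1% v 2%, 22.0 of 22.7 points are. At 2% v 4%, one or two deaths in total account for 7.2 of 13.6 points, and coverage given one or two deaths is 80.5%.

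**Equal true rates.** At 0.5%, 1% and 2% in both arms, Wald covers 99.98%, 99.8% and 98.7%. The shortfall needs unequal rates.

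**Continuity correction.** Adding 1/50 = 2.0 points per side brings coverage to 99.6% or more at the three unequal pairs, but gives only (-2.0%, 2.0%) at 0 v 0.

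**Agreement with Fisher.** At 0 v 4, Wald is (-15.5%, -0.5%), which excludes zero, while Fisher's p = 0.117. Newcombe is (-18.8%, 0.6%).

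**Admissions.** Wald coverage is 90.4% at an assumed 2.5% v 5%, 94.4% at 7% v 14% and 94.3% at 14% v 14%. For 3 v 7 admissions, Wald is (-19.7%, 3.7%) and Newcombe (-20.8%, 4.4%). For 7 v 7 they are (-13.6%, 13.6%) and (-14.1%, 14.1%).

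**The case against.** The SAP does not say Wald, and every death rate above is assumed. The low coverage at the two smaller rate pairs is almost entirely the 0 v 0 result, so it says little about one or two deaths. Newcombe covers more than 99% at these rates, so being narrower than Newcombe does not by itself make an interval too narrow. A continuity-corrected normal interval also fits the SAP's wording and covers well: at 0.5% v 1% its mean width is 8.8 points against 15.4. SAP 7.1 displays zero percentages as blanks, so the exact printed output is uncertain. The table will also carry the counts, causes of death, exact per-arm limits and Fisher's p. Protocol section 11 makes all analyses descriptive, and no decision rule uses this interval.

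Much of this stands, and it limits the harm. It does not remove the defect:

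- Pooled and unpooled standard errors both vanish at 0 v 0, and the corrected form allows only 2.0 points either way beside per-arm limits of 7.1%.
- At 2% v 4%, one or two deaths do produce misses, more than half of the total.
- The blank-display rule does not clearly extend to differences or confidence limits, and would not supply a valid interval if it did.
- The per-arm limits and Fisher's test give no interval for the difference.
- In a descriptive report, the interval is the main statement of uncertainty.

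**Conclusion.** The concern holds. On the natural uncorrected reading, the planned interval for the mortality difference is degenerate with no deaths. At 0 v 1 it is about half the width of a score-type interval (7.8 points, from -5.9 to 1.9, against 15.8, from -10.5 to 5.3). Coverage falls to between 53% and 86% at the assumed unequal rates; it does not fall when the true rates are equal, and a continuity correction restores it while leaving 0 v 0 far too tight. These sizes rest on 50 per arm and on assumed death rates.

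For admissions the wording matters only if events are few; around the background 14%, the normal approximation is acceptable. This is a reporting fault in one secondary endpoint, worth correcting but with limited consequences.

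**What to change.** In SAP 7.6.4.2, replace the closing reference to a normal distribution with a named method: a two-sided 95% Newcombe hybrid-score interval for the risk difference. A Miettinen-Nurminen or exact unconditional interval would also do. Make the same change in 7.6.4.1 for consistency. Settle it before unblinding, so that the method is not chosen once the death counts by arm are known.

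The cost is one phrase in each of two sections and one procedure option. Intervals become wider, clearly so for rare deaths and by about half a point per side at 7 v 7 admissions (14.1 against 13.6). Conflicts with Fisher's test become less frequent but do not disappear: at 0 v 5, Newcombe gives (-21.4%, -0.9%) while Fisher's p = 0.056.

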7.6.5 Exploratory Clinical Analysis

7.6.5.1 Time to Resolution of Symptoms

Symptom assessment will use a checklist provided to the subject with symptoms such as sore throat, cough, gastrointestinal symptoms (vomiting, diarrhea), anosmia, dysgeusia, other (specify), etc. Symptoms start date, end date (or ongoing), severity "None", "Mild", "Moderate", or "Severe" and symptoms status "Resolved", "Ongoing", or "Returned to Baseline" will be collected.

Resolution of symptoms is defined as new COVID-19 symptoms are completely resolved (i.e. status of "Resolved") and pre-existing non-COVID-19 symptoms return to baseline (i.e. status of "Returned to Baseline") reported on the eCRF of "COVID-19 Symptom Assessment". The time to resolution of symptoms is defined as the time (in days) from Day 1 to the first date where symptoms have been resolved. Subjects didn't achieve resolution of symptoms will be censored at the date of last assessment of symptoms. The median (95% CI) time to resolution of symptoms will be presented by treatment groups using the Kaplan-Meier method for the ITT population.

Statistical Analysis Plan

Sponsor Name: Clear Creek Bio, Inc.
Sponsor Protocol ID: CCB-CRISIS-02

Covance Study ID: 000000207395

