6.3 Exploratory Endpoints

Through Day 29:

- Time to viral clearance (two consecutive negative tests);
- Time to resolution of new onset COVID-19-related clinical symptoms and pre-existing non-COVID-19 symptoms returned to baseline;
- Time to clinical improvement measured by a favorable shift in WHO Ordinal Scale score for the subset of subjects with baseline WHO Ordinal Scale of 2.

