15 APPENDICES

15.1 Appendix A: CCB-CRISIS-02 Schedule of Events

CCB-CRISIS-02 Schedule of Events Windows are relative to first dose time Procedures	Screen (D -7 to -1) IPV ^f	D1 IPV	D2, 3 (± 8 hrs) TC ^f	D4 (± 8 hrs) TM	D5,6,7 (± 8 hrs) TC	D8 (± 8 hrs) IPV+TM	D12 (± 1 day) TM	D15 (± 1 day) IPV+TM	D22 (±1 day) TM	Final Visit D29 (± 2 days) IPV+TM
Informed Consent (note Date and Time)	X									
AE/Concomitant Medications (dose, route, duration or ongoing)	X	X	X	X	X	X	X	X	X	X
Medical history (relevant within one year or ongoing)/ History of current illness (date of symptom onset or change in baseline co-morbidity thought to be due to COVID-19 infection)	X									
Demographics (subject reported height and weight, date of birth, gender, race, ethnicity)	X									
Check for Physical Exam abnormalities (subject self-reported)	X									
Pregnancy Test (WOCBP)	X (serum)									X (urine)
Hematology/Chemistry ^a	X	X				X		X		
Vital Signs ^b	X	X		X		X	X	X	X	X
Symptom Assessment ^c	X	X		X		X	X	X	X	X
SARS-CoV-2 RT-PCR ^d	X									
Viral load sample (pre-dose Day 1) ^e		X		X		X	X	X	X	X
Hospital Status						X		X	X	X
WHO Ordinal Scale Assessment		X				X		X	X	X
Confirm Eligibility		X								
Randomize subject and dispense Study Medication		X								
Study drug administration ^f		X	X	X	X D5 Only					
Drug Accountability						X				

^aDo not repeat if within 48h of Day 1 visit. Send to Covance Central Laboratory Services (CCLS) for analysis.

^bVital signs include heart rate, respiratory rate, body temperature, and SpO2. Subject will be provided with a thermometer and pulse oximeter with heart rate monitoring capability. Training will be provided during the first visit. Vital signs parameters will be observed and recorded by study staff via telemedicine or in person (IPV) (at the study site or home visit).

^cSymptom Assessment will capture symptoms such as sore throat, cough, GI symptoms (vomiting, diarrhea), anosmia, dysgeusia, other (specify), etc. Severity None, Mild, Moderate, or Severe will be collected. Symptom(s) onset date must be within 7 days of first dose.

^dDocumentation of a positive SARS-CoV-2 result from RT-PCR or other FDA-approved test is required to qualify for Screening.

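### Read literally, the symptom-resolution rule in SAP 7.6.5.1 censors recovered subjects whose pre-existing symptom is coded 'Resolved', or 'Ongoing' at an unchanged level

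*SAP*

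**What the plan says.** SAP 7.6.5.1 collects start date, end date, severity and a status for each symptom; in its words, "symptoms status 'Resolved', 'Ongoing', or 'Returned to Baseline' will be collected". Resolution has two parts. New COVID-19 symptoms must have the status 'Resolved', and for the rest the condition is "pre-existing non-COVID-19 symptoms return to baseline (i.e. status of 'Returned to Baseline') reported on the eCRF". Time runs from Day 1 to the first date on which symptoms have been resolved. For the others the rule is: "Subjects didn't achieve resolution of symptoms will be censored at the date of last assessment of symptoms". The planned output is limited: "The median (95% CI) time to resolution of symptoms will be presented by treatment groups using the Kaplan-Meier method for the ITT population". No between-group test is named.

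Protocol v5.0, Section 6.3, gives the endpoint as "Time to resolution of new onset COVID-19-related clinical symptoms and pre-existing non-COVID-19 symptoms returned to baseline", with no status code attached. The Schedule of Events (Appendix A) has the history of current illness taken at Screening, including "date of symptom onset or change in baseline co-morbidity thought to be due to COVID-19 infection".

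**The concern.** The SAP's 'i.e.' equates the pre-existing condition with one code, and two kinds of recovered subject fall outside it.

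- **Pre-existing symptom that clears completely.** 'Resolved' is the natural code. That is a better outcome than a return to baseline, yet the rule does not accept it.
- **Chronic symptom that COVID-19 never changed.** It has nothing to return from. There is no 'unchanged' code, and 'Ongoing' is a plausible entry at each assessment.

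Both subjects would be censored at their last symptom assessment. The endpoint would then partly reflect chronic comorbidity rather than recovery from COVID-19. With about 15 sites and no coding rule in either document, the same patient could also be classified differently from site to site.

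**Working it through.** The plan states no event rate, power or expected median for this endpoint, so there is no figure to reproduce. The check has three parts.

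**1. The rule applied to each status.** Suppose that all new COVID-19 symptoms are 'Resolved'.

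| Pre-existing symptom on the form | Definition met, read literally? |
|---|---|
| None entered | Yes |
| 'Returned to Baseline' | Yes |
| 'Resolved' | No: censored |
| 'Ongoing' | No: censored |

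Two of the three codes block the endpoint. No other SAP section rescues these subjects: Section 6.2 (missing data) and Section 7.1 (general principles) do not address symptom status.

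**2. SAP against protocol.** The protocol asks only that pre-existing symptoms be back at baseline. A symptom that stayed at its usual level, or went away, plausibly satisfies that wording but fails the SAP's. So the SAP is the narrower of the two.

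**3. Illustration of size.** Both inputs are assumptions, since the documents give neither:

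- *f*, the share of subjects who recover but cannot meet the literal rule: 5% to 20%;
- median time to resolution under a rule without this problem: 10 days, exponential.

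If these subjects are censored around Day 29, the Kaplan-Meier curve before then estimates (1 − f)(1 − 2^(−t/10)) resolved by day t. The reported median solves

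(1 − f)(1 − 2^(−t/10)) = 0.5, so t = −10 × log2(1 − 0.5/(1 − f)).

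| f | 0.5/(1 − f) | Reported median (days) | Ratio to 10 days |
|---|---|---|---|
| 5% | 0.526 | 10.8 | 1.08 |
| 10% | 0.556 | 11.7 | 1.17 |
| 15% | 0.588 | 12.8 | 1.28 |
| 20% | 0.625 | 14.2 | 1.42 |

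For example, at f = 20%: 1 − 0.625 = 0.375, and −log2(0.375) = 1.415, so t = 14.2 days. The curve levels off at 1 − f, so at f = 50% or more the median would not be reached.

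For the added noise, take 50 subjects per arm and let the number of such subjects in each arm be binomial. The chance that the arms differ by 5 subjects or more (10 percentage points) is about 4%, 13%, 21% and 26% at f = 5%, 10%, 15% and 20%. A normal approximation agrees. At f = 10% the standard deviation of the difference is √(2 × 50 × 0.1 × 0.9) = 3.0, and with a continuity correction 4.5/3.0 = 1.5, a two-sided probability of 13%.

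**The case against.** The strongest reply is that the eCRF and its completion rules are not in the documents. A chronic symptom that did not change might be recorded only in medical history, which leaves the pre-existing condition empty. Or a site might code it 'Returned to Baseline' because it is at baseline. The verb 'return' also suggests that only symptoms that departed from baseline were meant. This stands in part: a reader might infer that such subjects can never meet the endpoint, and the documents do not establish that. It holds only when the symptom is entered on the form and coded 'Resolved' or 'Ongoing'. The reply does not remove the problem, because the outcome then rests on site coding that neither document fixes, and a program written to the SAP text would still reject 'Resolved'.

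A reader might also infer that a symptom worsened by COVID-19 is already at baseline on Day 1, because the SAP defines baseline for other variables as the last value before first dose. Section 7.6.5.1 does not use that definition. It relies on a reported status, and the Schedule of Events speaks of a "change in baseline co-morbidity thought to be due to COVID-19 infection", which points to the pre-illness level.

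Finally, a reader might infer a spurious treatment effect. The rule applies equally to both randomized arms, so an imbalance is chance, not bias. An imbalance of 5% against 15% moves the illustrative medians from 10.8 to 12.8 days, a gap of 2.0 days. With 50 per arm and the 10-day exponential, the standard error of one median is √(0.25/50) ÷ (0.5 × ln 2/10) = 0.0707/0.0347 = 2.0 days. For the difference it is 2.0 × √2 ≈ 2.9 days. The gap is under one standard error, and the planned 95% intervals reflect this kind of variation.

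**Conclusion.** The point holds as a literal-reading defect in a stated rule. SAP 7.6.5.1 accepts one code for pre-existing symptoms and so can censor subjects who have recovered, one group of them with an outcome better than baseline. The expected effect is longer and noisier medians in both arms, not a systematic difference between them. The 5% to 20% share and the 10-day median behind the 10.8 to 14.2 day range are assumptions; the true size depends on how common such subjects are and on site coding. The stakes are limited, because the endpoint is exploratory and only medians by group are planned. The change is still worth making, since it is cheap and the derivation should be settled before unblinding.

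**What to change.** In SAP 7.6.5.1:

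- count the pre-existing condition as met when the status is either 'Returned to Baseline' or 'Resolved';
- apply the condition only to pre-existing symptoms that worsened with COVID-19, so that an unchanged chronic symptom does not block resolution;
- state that baseline in this definition means the level before COVID-19.

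This costs two or three sentences in the next SAP version. Version 1 is dated 04 November 2020, before protocol v5.0 of 19 November 2020, and its Sections 8 and 9 already anticipate a later version. No new eCRF field is needed. The small downside is that identifying which pre-existing symptoms worsened relies on the history of current illness already taken at Screening.
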